**Table 1. Instruments**

Variable	Measurement
Demographic data	Gestational age, birth weight, maternal history, prenatal and perinatal complications and medication, mode of delivery, Apgar scores, resuscitation at birth and neonatal acuity (SNAP II) score, medications and disease processes associated with decreased intestinal motility, episodes and duration of KC
Nutritional factors (1-8) below	
1. Enteral intake	Weekly 24-hour enteral feeding intake in mL/kg for first 6 weeks; Type of feeding received
2. Time to full feeds	First day infant received $\geq 120$ mL/kg/d of enteral feedings
3. Hours of TPN	Number of hours infant received some PN for days 1-42
4. PNALD	Weekly or biweekly liver function tests (level of direct bilirubin, alkaline phosphatase AST and ALT) for first 6 weeks
5. Hours of central venous line access	Number of hours infant has a central venous line for days 1-42
6. Episodes of late onset sepsis	Episodes of culture proven or presumed sepsis (treated with 7-10 days of antibiotics but with negative cultures) during week 1- 6 weeks of life
7. Growth indices	Weekly weight, length, and head circumference
8. Length of hospital stay	Days infant remains in hospital from birth until discharge
Episodes of NEC	Episodes of radiologic evidence of NEC during the first 6 weeks
Gastrointestinal bleeding and inflammation (1-2) below	
1. Presence of blood in stools	Positive or negative guiac of all stools for first 6 weeks
2. Fecal calprotectin levels	Level of fecal calprotectin at 3 and 6 weeks
Gastrointestinal function	Serum levels of gastrin and motilin at 14-21 days
Respiratory aspiration of gastric contents (1-3) below	
1. Pepsin level in tracheal aspirates	Pepsin level in the tracheal aspirates of ventilated infants on day ,7,14, 21, 28 and 35
2. Presence of aspiration pneumonia	Presence of aspiration pneumonia on all radiographs
3. Presence of ventilator associated pneumonia	Presence of positive tracheal aspirate on ventilated infants

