**Sample and Setting.** The proposed study will follow a prospective cohort ( $N = 120$ ) of racially and economically diverse VLBW infants for 6 weeks following birth. The infants will be born to mothers who are English or Spanish speaking and who are 18 years of age or older. VLBW infants will be sampled by convenience from the neonatal intensive care unit (NICU) at Shands Children's Hospital, a Level III tertiary care center. The hospital is part of the University of Florida and includes a 52 bed NICU. The hospital catchment area encompasses north central Florida and southern Georgia, a predominantly rural and semi-rural population. Approximately 100-110 VLBW infants are delivered there per year. In the preliminary study, 70% of mothers consented for the study. Inclusion criteria for the infants are as follows: (1) born at 32 weeks or less of gestational age, (2) birth weight equal to or less than 1,250 grams, and (3) infant receiving some enteral feedings by 72 hours of age and parenteral feedings by 24 hours of age. Exclusion criteria for the infants are as follows: (1) congenital or chromosomal abnormalities, (2) complex congenital heart diseases and congenital anatomic gastrointestinal abnormalities, (3) Infants will be withdrawn from the study if any of the following occur: grossly bloody stools, radiologic evidence of NEC, or other intestinal complications such as perforation.

**Sample Size Determination / Power Analysis.** In the preliminary study, 40 premature, VLBW infants had a mean enteral intake at 14 days of 72 mL/kg/d ( $SD=65$ ). To detect a 50% improvement to 108, we would require 104 evaluable subjects in a non-sequential design for Primary 1.1 to achieve 80% power at  $P=0.05$  (two-sided). To accommodate one interim analysis, we employed the minimax method of Shuster et al (2002), with first look after 66 evaluable subjects have been accrued. If  $|Z|>2.28$  we shall stop for significance. If  $|Z|<1.12$ , the study will be reviewed for possible futility. There will be no stopping for futility. Otherwise, the study will accrue 120 evaluable subjects (54 more). No competing two stage design can achieve a lower worst case scenario average sample size than this one's 89 evaluable. Intent-to-treat will be followed as closely as possible. However, to accommodate dropouts including deaths (15%) and infants who develop NEC (7%) we expect to accrue 160 subjects.

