**Randomization.** Within 72 hours of life and within 24 hour of initiating feeds of less than 20 mL/kg/d, informed consent will be obtained from the mothers, and infants will be randomly assigned to one of two groups by random length permuted blocks of sizes 4, 6, or 8 to maintain approximate balance assigned to each treatment group.

**Standard Infant Feeding Protocol.** As per standard NICU protocol, all infants will begin receiving PN within 24 hours of life. In addition, all infants will have an orogastric (OG) or nasogastric (NG) tube placed upon admission to the NICU and begin receiving enteral feeding of less than 20 ml/kg/d within 72 hours. Length of insertion of the OG/NG tube is determined by measuring from the tip of the nose to the tip of the ear lobe and then halfway between the xiphoid process and umbilicus (Ellett et al., 2011). Minimum insertion length based on the weight of the infant (Cordero et al., 2011). If the infant receives an X-ray upon admission, placement of the OG/NG tube is verified. Placement is also verified if additional X-rays are taken during the study as per usual OG/NG placement protocol in the NICU. Depending on the infant's gestational age, weight, and clinical status, feedings are initiated at up to 20mL/kg/d and advanced daily by no more than 20mL/kg/d toward a goal of 120-150mL/kg/d divided into 8 equal feedings per day using the established University of Florida Children's Hospital NICU feeding guidelines. Mom's own breast milk is encouraged, and donor breast milk provided if mothers own breast milk is unavailable. Prior to each feeding, the OG/NG tube is checked for proper placement by the bedside nurse verifying the insertion length with the initial measured insertion length. In addition, the nurse assesses the infant for any signs or symptoms of feeding intolerance or NEC (i.e., abdominal distension and/or tenderness, increased abdominal girth, visible bowel loops, presence of emesis, and visible blood in the stool). It is standard protocol to aspirate RGC prior to each feeding. However, for this study, this will only occur in infants randomized to Group 1. Kangaroo Care (holding of an infant dressed only in a diaper upon someone's bare chest) can positively affect growth and improve feeding tolerance (Conde-Aquedelo et al., 2011) Kangaroo care is encouraged in this NICU and nursing protocols have been established to provide support to all mothers regarding provision of kangaroo care.

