**Aim 3.** Aim 3 will determine the effect of routine RGC aspiration on gastrointestinal function as evidenced by gastrointestinal peptide activity. Serum levels of gastrin and motilin will be measured on all infants between 14 and 21 days depending upon the timing of a routine blood draw. Since all GRCs are not discarded, waiting until between 14-21 days will allow adequate time for potentially one or more GRC to be discarded. 1 mL of blood will be taken during a routine blood test. All samples will be sent to the laboratory at Shands Children's Hospital at the University of Florida for testing, and lab values will be extracted and recorded by the project coordinator.

**Statistical Analysis.** Data will be entered into the RedCap system by the research assistant. For the primary hypothesis (P1.1), the total weekly enteral intake will be compared between the two randomized treatment groups via a two-sided Welch-corrected T-test. For sample sizes of this magnitude, the central limit theorem assures us that this is an assumption-free analysis, even if the underlying population variances differ. An interim analysis of P1.1 will also be done as described in the Power Analysis section below. Secondary hypotheses S1.1-S1.7 will be tested in the same manner as the primary hypothesis P1.1. For secondary Hypothesis S2.1 (S3.1), [S3.2], we shall compare the personal fractions of positive stools (gastrin levels) [motilin levels] respectively via two-sided Welch-corrected T-tests. For secondary hypothesis S2.2, we shall use a repeated measures analysis of variance to compare the groups with respect to week 3 and week 6 calprotectin levels. . Actual P-values will be reported, and each hypothesis will be accompanied by a point estimate and 95% confidence interval estimate for effect size. For descriptive purposes, a P-value of under 5% will be declared significant. The study is powered strictly around the primary hypothesis P1.1. Withdrawal rates will be compared between the treatments in a tertiary manner using survival analysis (time to withdrawal), via a logrank test.

**Expected outcomes.** Based on the preliminary study, it is reasonable to expect that infants who do not receive routine aspiration of RGC will have better nutritional outcomes, evidence of less gastrointestinal bleeding and inflammation, and improved gastrointestinal function.

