**Table 2: Timetable for Collection of Data**

Data	Time Period Collected
Demographic data	Upon entry into study and during 6 week study period
24-hour enteral feeding intake in mL/kg	Weekly for 6 weeks
Time to full feedings	Recorded daily until 120mL/kg/d reached
Hours of PN	Daily for 42 days
Evidence of PNALD	Weekly or biweekly liver function tests (level of direct bilirubin, alkaline phosphatase AST and ALT )for first 6 weeks
Hours of central venous line access	Daily for 42 days
Episodes of late onset sepsis	All incidences of culture proven or presumed (treated for 7-10 days but with negative cultures) for weeks 1-6.
Growth indices	Weekly weights, head circumferences and lengths
Days to discharge	Days infant is hospitalized
Episodes of radiologic evidence of NEC	All incidences for 6 weeks
Results of stool guaiac	Every stool for 6 weeks
Fecal calprotectin levels	3 and 6 weeks
Serum levels of gastrin and motilin	14-21 days
Pepsin level of respiratory aspirate	Day 1,3,5,7,14 21, 28 and 35 in ventilated infants
Evidence of aspiration pneumonia	All radiographs for 6 weeks
Respiratory cultures	All respiratory cultures done on ventilated infants for 6 weeks

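### The tables collect enteral intake as one 24-hour value per week: this forgoes precision and does not supply the weekly total that the analysis text tests

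*Combined protocol and SAP*

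**What the plan says.** Table 1, row 1, records enteral intake as "Weekly 24-hour enteral feeding intake in mL/kg for first 6 weeks". Table 2 lists the 24-hour intake in mL/kg with the frequency "Weekly for 6 weeks". Other rows of Table 2 are daily: PN hours and central line hours are collected on each of 42 days, and time to full feedings is "Recorded daily until 120mL/kg/d reached".

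The Statistical Analysis section describes the primary test (P1.1) differently: "the total weekly enteral intake will be compared between the two randomized treatment groups via a two-sided Welch-corrected T-test".

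The Sample Size Determination / Power Analysis section uses a daily quantity at one time point. It reports that "40 premature, VLBW infants had a mean enteral intake at 14 days of 72 mL/kg/d", with an SD of 65, and continues: "To detect a 50% improvement to 108, we would require 104 evaluable subjects in a non-sequential design".

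The Standard Infant Feeding Protocol advances feeds by at most 20 mL/kg/d each day "toward a goal of 120-150mL/kg/d divided into 8 equal feedings per day".

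The documents do not say which day of the week is read, which of the six weeks is primary, or how daily or weekly readings become one value per infant.

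**The concern.** If the tables are followed, a week of feeding is represented by a single day. An infant who advanced well but was held throughout the reading day scores zero. An infant held for most of the week but fed on that day scores well. The trial compares two policies that may differ in how often feeds are interrupted, since clinicians see gastric residuals in Group 1 when making feeding plans. A one-day reading registers an interruption only if it falls on that day, whereas a weekly mean counts interruptions by their duration.

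Two things are at stake. The first is precision: any day-to-day variation within an infant adds to the SD of a single-day value and would be partly averaged out over several days. The second is consistency: an analyst working from the tables has no weekly total to test, and an analyst working from the Statistical Analysis section has a variable whose SD the power section does not give.

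**Working it through.** **Inputs from the documents.** Mean 72 and SD 65 mL/kg/d at 14 days, target 108 (difference 36), two-sided 0.05, 80% power, 104 evaluable (Sample Size section). Eight feeds a day (Standard Infant Feeding Protocol). Equal allocation is read from the permuted-block description.

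**Not in the documents.** The correlation rho between an infant's intakes on different days of the same week. I use 0.6 to 0.95, with equal SD on each day and equal correlation between any two days.

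**1. The plan's own figure.** Per arm, n = 2 × SD² × (1.96 + 0.84)² / difference² = 2 × 4225 × 7.849 / 1296 = 51.2 (7.849 uses unrounded normal quantiles). This rounds up to 52, or 104 in total. The stated figure reproduces, and noncentral-t power at 52 per arm is 79.9%.

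**2. What a hold does to the reading.**
- One missed feed of eight on a 72 mL/kg day: 72 × 7/8 = 63.
- A hold of the full 24 hours: 0 on a single-day reading.
- The same full-day hold in a week otherwise steady at 72: 7-day mean = 72 × 6/7 = 61.7.

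**3. Precision of a 7-day mean, difference kept at 36.** SD of the mean = 65 × √((1 + 6 rho)/7).

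| rho | (1 + 6 rho)/7 | SD | Power at 104 |
|---|---|---|---|
| single day | 1 | 65.0 | 79.9% |
| 0.6 | 0.657 | 52.7 | 93.2% |
| 0.8 | 0.829 | 59.2 | 86.7% |
| 0.9 | 0.914 | 62.2 | 83.3% |
| 0.95 | 0.957 | 63.6 | 81.6% |

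If correlation instead decays with the gap between days (first-order autoregressive), an adjacent-day value of 0.9 gives about 88% and 0.95 gives about 84%.

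**4. If averaging shrinks the difference.** Intake is rising around day 14, so a window mean need not show the full day-14 difference. Taking 35 and 34 as assumed values:
- rho 0.8: 84.8% and 82.7%, a gain of 3 to 5 points over 79.9%.
- rho 0.9: 81.2% and 78.9%, about nil.
- rho 0.95: 79.4% and 77.1%, nil or a small loss.

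The break-even difference is 36 × √((1 + 6 rho)/7): 29.2, 32.8, 34.4 and 35.2 for rho 0.6, 0.8, 0.9 and 0.95. At a difference of 30 and rho 0.8, power falls to 73%.

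**5. At the planned maximum.** With 120 evaluable infants and the single-day SD of 65, fixed-sample power is 85.3%. With the look at 66, no futility stop and an assumed final boundary of 2.09 (chosen to hold overall alpha at 0.05), it is about 84%.

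**The case against.** The strongest reply is that the analysis text already speaks of a weekly total. If that means the sum of seven daily intakes, the primary value does not rest on one day. With all seven days observed, testing the sum is the same as testing the mean, because the two differ only by a factor of 7. This stands to the extent that the documents do not settle what P1.1 is, so a reader should not conclude that the primary value is certainly a single-day reading. It does not rescue the plan, because Tables 1 and 2 do not collect the days that such a sum needs, and the power inputs are in mL/kg/d at 14 days.

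A second reply is that the size of the gain is unknown. A reader might take the large SD as proof of day-to-day noise: with a mean of 72 and an assumed ceiling of 150, the largest possible SD is √(72 × 78) = 74.9, and 65 is 87% of it. That inference fails. The ceiling is the top of a goal range, and the same spread arises if some infants are steadily near full feeds and others are barely advancing. Correlation would then be high and averaging would gain little. The 20 mL/kg/d limit on daily advancement also makes large upward jumps between adjacent days unlikely. This objection stands, and it is why the result is given as a range.

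Third, a window running past day 14 can be cut short by death or by withdrawal for the reasons listed under Sample and Setting. That is fair, and the fix has to include a scoring rule.

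**Conclusion.** The point holds as a design improvement joined to an inconsistency. The inconsistency is firm: the tables collect one 24-hour value per week, and the analysis text tests a weekly total that those values cannot supply. The precision gain is conditional. At 104 evaluable it runs from about 2 points (rho 0.95) to 13 points (rho 0.6) if the difference stays at 36. If the difference shrinks to 34-35, it is 3-5 points at rho 0.8 and about nil at 0.9 or above. These figures rest on an assumed correlation, a common daily SD, and SD 65 being a single-day value, as its units and time point suggest.

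Two stronger readings are tempting and not supported:
- That the trial is underpowered. If 65 is the single-day SD, the 104 already allows for that noise, and the design can continue to 120 evaluable.
- That one held feed can bring the reading close to zero. With eight feeds a day, only a hold of about the full 24 hours does so.

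**What to change.** - In Table 1 (row 1) and Table 2, abstract the charted 24-hour intake for each day of a stated 7-day window at day 14: days 11-17, or days 8-14 if no later data are wanted. If the groups are still diverging, the earlier window may shrink the difference more, so the break-even values above matter in choosing it.
- Define P1.1 as the infant's mean daily intake in mL/kg/d over that window, and reword the Statistical Analysis section to match.
- State how infants who die or are withdrawn within the window are scored, for example by the mean of the available days.
- Keep the single day-14 reading as a sensitivity analysis.
- If the pilot's daily charts are available, compute the SD of the 7-day mean and the day-to-day correlation from them, and restate the power on that basis.

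The cost is seven charted totals per infant instead of one for that window, with no extra infants, samples or change in care. Daily intake already has to be followed until 120 mL/kg/d is reached; after that point the remaining days of the window would be additional abstraction. The estimate would describe intake around day 14 rather than on day 14 exactly. Until the pilot charts are checked, the SD of the new variable is an assumption rather than a pilot estimate.

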**Table 2: Timetable for Collection of Data**

Data	Time Period Collected
Demographic data	Upon entry into study and during 6 week study period
24-hour enteral feeding intake in mL/kg	Weekly for 6 weeks
Time to full feedings	Recorded daily until 120mL/kg/d reached
Hours of PN	Daily for 42 days
Evidence of PNALD	Weekly or biweekly liver function tests (level of direct bilirubin, alkaline phosphatase AST and ALT )for first 6 weeks
Hours of central venous line access	Daily for 42 days
Episodes of late onset sepsis	All incidences of culture proven or presumed (treated for 7-10 days but with negative cultures) for weeks 1-6.
Growth indices	Weekly weights, head circumferences and lengths
Days to discharge	Days infant is hospitalized
Episodes of radiologic evidence of NEC	All incidences for 6 weeks
Results of stool guaiac	Every stool for 6 weeks
Fecal calprotectin levels	3 and 6 weeks
Serum levels of gastrin and motilin	14-21 days
Pepsin level of respiratory aspirate	Day 1,3,5,7,14 21, 28 and 35 in ventilated infants
Evidence of aspiration pneumonia	All radiographs for 6 weeks
Respiratory cultures	All respiratory cultures done on ventilated infants for 6 weeks
